
Randomized Controlled Trial of *Game Changers*

Overview. The proposed design is an individually randomized group-treatment trial using a clustered design.⁹⁶ We will recruit 210 PLWH and randomize 105 to the intervention and 105 to a no-intervention control arm. Each PLWH will be asked to recruit social network members (alters to whom they have disclosed) (736 total, 368/arm). All participants will complete assessments at baseline, and 6, 12 and 18 months post-baseline to assess improved HIV prevention behaviors within the network, mediators of improved behaviors, and HIV outcomes. Participants will be divided into 7 cohorts of 30 (within each cohort, 15 intervention and 15 control). Intervention implementation for the 7 cohorts will be staggered, such that two will be conducted at a time (i.e., 60 PLWH and 210 alters for two cohorts at a time), except the last wave in which there will be one cohort of 30. [name] will oversee the implementation of the intervention program, while [name] will oversee the assessment, data collection and analysis components of the trial.

Randomization. A blocked 1:1 randomization design with stratification by gender (with randomly alternating blocks of 2, 4, and 6 to prevent anticipation of condition) will ensure balance across arms. All groups will be mixed sex (with approximately equal numbers of men and women/group), and a male and a female facilitator will conduct each group. The statistician will use a random number generator to devise a randomization log and a set of sealed numbered randomization envelopes (to prevent condition foreknowledge). After completing the baseline survey, the interviewer will open the corresponding envelope and record the condition. Although individual randomization entails contamination risk, this type of group intervention—where recipients attend several sessions that use structured content and group interaction to target multiple aspects including internalized stigma, comfort and skills with disclosure, and how and who to engage in advocacy with—is less conducive to contamination. Statistical models suggest $\geq 30\%$ of the control arm must receive the equivalent of a full-strength intervention to result in meaningful contamination,⁹⁷ so with a

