multi-component, multi-session intervention like Game Changers it is highly unlikely that casual communication between intervention and control participants could result in meaningful contamination. We will assess and control for whether control participants communicated with intervention peers about intervention content.

Eligibility Criteria for PLWH include (1) ≥ 18 years-old, (2) in care for > 1 year (because they are more likely to be medically stable, adjusted to their HIV diagnosis, and ready to engage in advocacy), and (3) disclosed their HIV status to at least one person. All PLWH also will be patients at IDI's clinic, where they will be recruited. Clients will be excluded if they participated in the intervention as part of the prior R34 pilot study.

Eligibility Criteria for Alters include (1) ≥ 18 years-old; (2) referred by a PLWH enrolled in the study; (3) know the PLWH's serostatus; and (4) willing/able to do the first study visit in person. (After initial screening/baseline visit, other alter study visits can be done by phone, or interviewers can travel to meet alters.) As described below, PLWH will be asked to recruit up to 4 alters for participation in assessments.

Recruitment. As in the pilot, to recruit PLWH: (1) clinic staff and expert patients (who work with clinic staff to track patients) will refer eligible patients to interviewers, who will be in the waiting area of the clinic on weekdays (M-F) every day during the recruitment period for each cohort; and (2) interviewers (who will be IDI staff) will approach all patients in the waiting area on the same designated days, to inform them of the study. Interviewers will cross-check the names of referred patients with IDI clinic records to verify that they are patients at IDI who have been in care for > 1 year and disclosed to at least one person. In the pilot, only one person was screened ineligible due to the disclosure criterion. Because we will enroll two intervention-control cohorts at a time, we need to recruit 60 participants at a time (30 per cohort) or per wave of recruitment; each wave of recruitment will take place over 3 months (30 PLWH and 105 alters enrolled and surveyed per month, 1.5 PLWH and 5-6 alters per day), followed by a 3-month period when the intervention and attention control program are implemented with the two cohorts, and no further recruitment until the next wave of recruitment in the next quarter (see Timeline).

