PrEP Use among alters. PrEP is currently only available to key populations, so only a subset of uninfected alters will be able to access it. If alters report taking PrEP, we will ask where they obtain PrEP, the date PrEP was initiated and self-reported adherence using an adapted Visual Analog Scale for ART Adherence.¹⁰⁵ If the alter receives PrEP at IDI, we will obtain medial release to confirm PrEP use with medical records.

HIV Outcomes. For PLWH participants and HIV-positive alters, we will obtain medical release to abstract HIV viral load and HIV diagnosis date from medical records. Because all PLWH will be patients at IDI, we will be able to obtain medical chart data easily. Self-reported ART adherence¹⁰⁶ as well as engagement in HIV care (number of HIV care visits attended during each follow-up period) will also be assessed.

Potential Mediators. For both PLWH and alters, Prevention Advocacy will be assessed with a scale developed for our pilot, measuring the extent to which participants discussed different HIV-related topics (e.g., HIV testing, PrEP, condom use, ART use) with people they know in the past 6 months (1=not at all to 5=very much; $\alpha=.87$ PLWH, $\alpha=.90$ alters); PLWH and alters also will be asked about discussions with each other. Among PLWH, we will assess Internalized HIV Stigma (Internalized AIDS-Related Stigma Scale, $\alpha=.69$)¹⁰⁷ and HIV Disclosure (if they have disclosed to some, none, or all family and friends in separate questions¹⁰⁸).

Potential Covariates/Moderators: Both PLWH and alters will be asked Socio-Demographic Characteristics (age, sex, education, work status, income, relationship status). PLWH will additionally be asked Medical Characteristics (HIV diagnosis date), Health-related Quality of Life [physical health ($\alpha=.81$) and mental health ($\alpha=.89$) items from PROMIS],¹⁰⁹ Competing Needs for Care (e.g., taking care of someone else),¹¹⁰ social support (from the MOS Social Support Survey, $\alpha=.78$),¹¹¹ and depression (PHQ-9, a validated screener).¹¹²

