Aims 1-3. Primary analyses will use a standard intent-to-treat approach, applying generalized mixed models (linear for continuous outcomes; logistic for binary outcomes) to the repeated-measures data to examine how intervention effects change over time, using an indicator for study arm, timepoint (baseline vs. follow-up), and timepoint by arm interaction to indicate whether change differs between arms. Our statistical methods will be consistent with advances in the analysis of personal network research,^{66, 135-137} accounting for any correlation among participants in the same intervention group sessions, and among alters referred by the same PLWH (ego), by adjusting standard errors for statistical inference tests with a sandwich estimator as implemented in SAS v 9.4.^{96, 138-141} We will use imputation for item nonresponse and account for non-random dropouts using logistic regressions that assign weights to retained participants that are inversely proportionate to the predicted probability of the participant being retained; if dropout is random, analyses will incorporate design effects. In follow-up analyses, we will explore interactions between each potential moderator and arm, including sex (of ego and/or alter, and concordance between the two) to examine if these variables moderate the intervention effects. If interactions with categorical moderators are significant, we will conduct post-hoc simple main effects t-tests with Bonferroni corrections. For continuous moderators,¹⁴² we will graph significant interactions at low and high levels of each score (± 1 SD). We will conduct post-hoc simple main effects t-tests with Bonferroni correction by comparing differences between discrete points on the regression lines. If *Game Changers* shows significant effects on hypothesized mediators (Aim 3), to test mediation we will compare: (a) Aim 1 models, adding baseline measures of mediator(s); and (b) the same models as in (a), adding post-intervention measures of mediator(s).¹⁴³ We will examine whether including post-intervention mediator(s) in (b)

decreases the coefficient for intervention effects on outcomes relative to the corresponding coefficient from (a). We will use a bootstrapping approach to test whether mediators account for effects.^{144, 145}

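### The plan would adjust for control participants' contact with intervention peers, a post-randomisation, control-only variable. This is not reconciled with the intent-to-treat model and, in some forms, can bias the arm effect.

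*Combined protocol and SAP*

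**What the plan says.** In *Randomized Controlled Trial of Game Changers*, the Randomization paragraph discusses contamination. It cites models under which at least 30% "of the control arm must receive the equivalent of a full-strength intervention to result in meaningful contamination", and concludes that "it is highly unlikely that casual communication between intervention and control participants could result in meaningful contamination". It then adds: "We will assess and control for whether control participants communicated with intervention peers about intervention content". The commitment is unconditional. It names no outcome, model, coding or time point, and does not say whether the adjustment is primary, secondary or sensitivity.

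The same paragraph fixes when allocation happens: "After completing the baseline survey, the interviewer will open the corresponding envelope and record the condition".

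*Statistical Analysis, Aims 1-3* gives the primary model: "Primary analyses will use a standard intent-to-treat approach, applying generalized mixed models", "using an indicator for study arm, timepoint (baseline vs. follow-up), and timepoint by arm interaction to indicate whether change differs between arms". No contact term appears there, and contact is not among the variables under *Potential Covariates/Moderators*. The assessment sections describe no item on contact with intervention peers. The advocacy items cover talk about HIV with people the respondent knows, and talk between a PLWH and that person's own alters.

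**The concern.** Contact with intervention content is something a control participant does, or does not do, after allocation. As worded, it has no counterpart in the intervention arm. Putting it in an effect model splits the randomised control arm by later behaviour, and can make the controls without contact the reference group for the whole intervention arm. If those who communicate differ in prognosis, the two sides are no longer exchangeable, and a difference can appear when the course does nothing.

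Selection of this kind is plausible. *Initial Formative Research* reports that advocacy by PLWH went with lower internalized stigma and with more disclosure, condom use, adherence and care engagement. Controls who talk about HIV with peers may therefore be people who were going to do better. Contact is plausible too: all PLWH attend one clinic, the arms run side by side within cohorts, and in the pilot 15 of the 135 alters whom the team tried to contact were already enrolled as PLWH. That last figure shows that participants know one another; it is not a contact rate.

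**Working it through.** **Inputs from the plan** (*Statistical Power*): 65% of control alters reporting condomless sex at month 18; 736 alters, about 625 after attrition; 210 index participants. **Assumed, because the documents give neither:** s, the share of controls with contact; d, the outcome gap between controls without and with contact that is due to selection alone. Two-sided alpha of 0.05 is also assumed.

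**The plan's own figure.** Mean cluster size is 625/210 = 2.98. Effective sample size is 625/(1 + 1.98 × 0.01) = 612.9 for ICC .01 and 625/(1 + 1.98 × 0.05) = 568.8 for ICC .05, matching the stated 612 and 568. I use 612, or 306 per arm. The plan gives no contact rate to reproduce.

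**Follow-up contrast, no true effect.** Let n and t be the rates in controls without and with contact, with n − t = d. Then 0.65 = s·t + (1 − s)·n, so n = 0.65 + s·d. With the contact term in the model, the arm coefficient is the intervention rate minus n: 0.65 − (0.65 + s·d) = −s·d.

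The chance of a significant false benefit is P(Z > 1.96 − s·d/SE), where SE² = 0.65 × 0.35/306 + n(1 − n)/[306(1 − s)]. For s = 20% and d = 20 points, n = 0.69, SE = √(0.000743 + 0.000874) = 0.0402, s·d/SE = 0.995, and the chance is 16.7% against a nominal 2.5%.

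| s | d (points) | n | False difference (points) | Chance of false benefit |
|---|---|---|---|---|
| 5% | 10 | 65.5% | 0.5 | 3.3% |
| 10% | 10 | 66% | 1.0 | 4.4% |
| 10% | 20 | 67% | 2.0 | 7.3% |
| 20% | 10 | 67% | 2.0 | 7.1% |
| 20% | 20 | 69% | 4.0 | 16.7% |
| 30% | 10 | 68% | 3.0 | 10.7% |
| 30% | 20 | 71% | 6.0 | 30.6% |

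If d is negative, the same sizes favour control.

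**The plan's test is the timepoint-by-arm term, so the form of the adjustment matters.** On a linear scale:

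- *Time-constant main effect:* it shifts a person's baseline and follow-up equally, so the difference in change is untouched.
- *Term switched on at follow-up:* the control change becomes follow-up in non-communicators minus baseline in all controls, so the bias is again −s·d.
- *Main effect plus contact × time:* only non-communicators' change is used, so bias arises only if communicators would have changed differently.

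**Simulation with no true effect.** There were 800 runs per setting, with 210 index participants, 3 alters each, baseline and one follow-up. The model was a logistic independence GEE with sandwich errors clustered by index participant, standing in for the planned mixed model. Strength of selection was assumed. False-benefit rates, with communicators better in both level and change:

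| Form | 20% communicating | 30% communicating |
|---|---|---|
| No contact term | 3.3% | 3.3% |
| Time-constant main effect | 3.3% | 3.3% |
| Main effect plus contact × time | 5.5% | 7.0% |
| Term switched on at follow-up | 11.0% | 15.9% |
| Follow-up-only contrast, adjusted | 13.4% | 16.4% |

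With selection on level only, at 30%, contact × time gave 3.1%, the switched-on term 8.1% and the follow-up-only contrast 7.4%. With no selection, every form stayed at 1.5-3.5%. Monte Carlo standard error is about 0.6-1.3 points.

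**The case against.** The only passage that specifies the primary model declares intent-to-treat and lists its terms, and contact is not one of them. The sentence on contact sits in the randomisation text and could describe a sensitivity analysis. A reader might infer that the primary analysis is already not intent-to-treat; the documents do not establish that. They establish an unqualified commitment to adjust that is not reconciled with the stated model.

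The s × d arithmetic belongs to a follow-up contrast or a term switched on at follow-up. For the planned timepoint-by-arm test, stable differences in engagement cancel if contact is a time-constant term. This stands, but it does not rescue the sentence: such a term would not correct contamination. Contact about course content cannot precede the course, so coding it from follow-up onward is the natural choice, and that form is open to bias.

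The plan also expects little contamination, and with s = 5% and d = 10 points the false difference is only 0.5 points. That too stands as a limit on size. But the plan's 30% threshold concerns full-strength exposure. The adjustment concerns any communication, which could be more common, and which marks a self-selected group even if it has no effect.

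**Conclusion.** The point holds as a conflict between two stated rules, with a conditional bias. Following the contamination sentence in an effect model would depart from the intent-to-treat comparison. Bias in the arm effect needs two things: a form that acts at follow-up, and controls who communicate having a different prognosis (for contact × time, a different change). For a follow-up contrast its size is s × d: 0.5-6 points over the assumed s of 5-30% and d of 10-20 points.

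Two further inferences are tempting and unsupported:

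- *That the error must favour the intervention.* The formative findings make this plausible, but they concern advocacy by PLWH and PLWH's own outcomes, not controls' contact with intervention peers or alters' behaviour. If communicators would have done worse, the error favours control.
- *That the adjustment covers index PLWH only and so misses alters.* The documents sometimes use the word participants for both groups, as under *Potential Benefits to Study Participants*, so the scope is unclear rather than shown to be too narrow.

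**What to change.** In the Randomization paragraph, delete the words *and control for*. In *Statistical Analysis, Aims 1-3*, state that the primary intent-to-treat model contains no contamination term and keeps all controls.

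Report descriptively the share of controls who had contact with intervention content, saying whether this covers index PLWH, alters or both. Add the contact item to the assessment description, since at present only the word *assess* implies that one exists.

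If a contamination-adjusted estimate is wanted, label it as a pre-specified secondary or sensitivity analysis, for example an instrumental-variable or complier-average estimate with randomised arm as the instrument, a defined exposure measure and its assumptions stated.

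The core change costs a few words. The contact item adds a little interview time, and an instrumental-variable analysis needs more, because exposure must be measured in both arms. The downside is that, if contamination is real, the primary estimate is somewhat diluted.
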